The researchers will deliver the Intervention with the patients participating in the study at leaving points, during the patient's journey through the COPD service, as specified in the diagram below. Patients enter the pulmonary rehabilitation (PR) section of the COPD service post-acute episode or by GP referral. Patients are then clinically assessed for suitability to continue in the exercise component of the service. If patients are deemed suitable for exercise then they continue onto PR. Post PR they have a review, 30 minutes with a clinician to ascertain their progress through the programme and to recommend continuation of exercise. At this point patients can also leave the programme.

Furthermore patients are offered maintenance exercise therapy – and are reviewed yearly, during these reviews other exercise and activity can also be recommended, patients can also leave the service at this point. These transition points in the care pathway; leaving the PR programme, or at

yearly maintenance review patients will be offered to participate in the GENIE study and provided with study information.

1. Those patients completing a PR programme, and in whom we wish to provide clear direction and signposting to appropriate social activity
2. Those who have benefitted from maintenance for 1 year or more, but at review could be encouraged to do more and have more social outlets.

Currently, patients leaving PR classes are usually offered the option to join the maintenance exercise class, delivered by the COPD team, other exercise options are considered, however, these options are currently limited or difficult to access in one place.

Building capacity to carry out the evaluation: Ensuring the GENIE database contains an appropriate library of social and health activities suitable for the Southampton COPD patient. The lead researcher will investigate existing exercise, social and community activities, then populate and categorise the GENIE database.

Introducing the intervention: In order to successfully implement the GENIE tool into clinical practice; the clinical team needs to be at the core of the process in order to ensure appropriate and effective facilitation. Therefore, the clinical team will be briefed as the study progresses, through question and answer sessions and direct learning opportunities in how the tool works and the objectives of the study.

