Selection and patient information: Patients in the COPD service; at the outset of their assessment, the end of PR and during maintenance sessions will be informed that the GENIE implementation evaluation is in progress.

Patients participating in these aspects of the service will be offered the opportunity to volunteer for the study, by the clinical team. If patients are interested they can then provide their names to the clinical staff to keep on a secure Solent database. Patient information sheets and invitation letters will be given out to the interested patients at their clinical visits to minimise postal and /or extra visits.

Once patients have received an information sheet, they will be allowed at least 72 hours to read and digest the information, (patient information sheets, consent and GP letters are separate documents), and share this with their friends and family if they wish to. Ideally, patients are provided with information in their clinical visits and are returning for clinical visits then appointments for research could be amalgamated with usual clinical visits. In this way extra study visits can be reduced. Patients, now participants, will be invited to consent and be randomised at the point of leaving usual clinical care. Furthermore, all patients at this point will have the opportunity to opt out of the study.

Once the participant is randomised (using block randomisation technique in clinic), then they will all receive normal clinical care (discharge planning with suggested activities), and the GENIE tool intervention, in the GENIE group, this is in addition to usual clinical care. Baseline questionnaires will also be administered at this visit.

The follow up period will commence 3 months (12 weeks) (+/- 1 week) from the day the GENIE tool was initially delivered. Participants will be invited back, via letter and /or phone call to attend their three month follow up visit at Bitterne Health Centre.

Solent NHS Trust will be the overall NHS organisation with one venue for study delivery; Bitterne Health Centre.

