Stage 3: This section will then link individuals to prioritised and valued activities and resources (links are to a pre-created database where local organisations and resources have been categorised).

Stage 4: The GENIE Tool then presents options in a user-friendly way, on a Google map with clear details about access, an example below:

Both groups will receive usual care, however one arm will have the addition of the intervention both will be called for a review at:

Three monthly follow up (+/- 1 week)

Six questionnaires will be administered. EQ-5D, health utilisation questionnaire, HEIQ and wellbeing questionnaires (CAT, GAD, PHQ-9), as well as the optional health behaviour questionnaire, so in 30 participants this will be seven, these will be repeated at 3 months post intervention (+/- 2 week). Furthermore, for those in the intervention arm, feedback and reflection discussions will be initiated using the network diagrams. Participants will be asked again for their permission to tape record these discussions to ensure parity and quality assurance between researchers.

Analysis of Outcomes

The study gathers data from the intervention arm and the non-intervention arm at baseline and 3 months post intervention. Results will be compared between the groups at baseline and 3 months post intervention. An economic analysis will be performed using a modified version of the Client Service Receipt Inventory (CSRI) (Beecham and Knapp 1999) Medication, health service use will be measured at baseline, 3 months post implementation and follow up. The modified version has been tailored to capture the needs of the target population (COPD patients). The CSRI has been widely used in previous research studies and has been evidenced as a valid measure of frequency of health service use (Patel 2005). The EQ5D is included to assess health status of patients during the GENIE intervention. Wellbeing score (CAT) and HEIQ and in the optional sub-group health behaviours (dietary intake, appetite, alcohol consumption and smoking habits) will be compared at baseline and 3 months. Furthermore, patient uptake of the social activities is to be recorded on paper using the Genie tool and compared between groups.

Rationale for the service implementation and evaluation design

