Participation in the study will be offered to every patient in pulmonary rehabilitation or maintenance exercise programs in the east of Southampton. Participants must also fulfill the inclusion criteria. Patients already referred into pulmonary rehabilitation groups will be approached and asked if they wish to participate in the study at assessment and at the end of pulmonary rehabilitation in their post PR review appointment. The appointments are offered to patients after completion of the patients PR program, usually after 12 sessions by the clinical team. Therefore, it is envisaged that a minimum of 30 patients per arm will be recruited; these include PR leavers, maintenance reviews referrals. Appointments will be offered in person, via the telephone with confirmation letter or text. The numbers from each of these groups cannot be predicted as it is dependent on clinical opinion, however the aim to have a minimum of 30 participants, with the aim to recruit up to 60 to ensure meaningful analysis.

Inclusion criteria;

- adults between 18 and 95 with a predominant diagnosis of COPD
- Ability to understand spoken English
- Enrolled in PR or maintenance therapy
- Ability and capacity to make their own decision and consent freely

Exclusion Criteria;

- No clear COPD diagnosis
- Inability to consent

The Intervention

This evaluation aims to demonstrate the effectiveness and increase social interactions and community networks in the COPD population in Southampton city.

Rational for GENIE is connecting people to new resources

The aim of using GENIE is to connect people with long-term conditions to local and (in the future) online resources to support them in their everyday lives. Objectives of GENIE:

- Raise awareness of the links and functions that social networks enable (for individuals and local community groups and organisations).
- Use social networks to engage patients in reflecting on their needs and support, support access to further resources and knowledge and introduce practices related to lifestyle, illness management, and behaviour change.
- Strengthen existing individual and community networks and improve patient engagement.

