- c) Clinical comparative analysis pre and post intervention including burden of disease (CAT score) and psychological impact of the disease, using Wilcoxin Ranked tests. Pre intervention burden of disease correlated with 3 months (+/- 1 week) disease burden post intervention (CAT), with significance.
- d) Clinical comparative analysis between groups at 3 months (as above) Wilcoxin Ranked tests.

12 month follow up survey

- a) Pre intervention burden of disease compared with 12 months disease burden post intervention (CAT).
- b) Activity uptake rates; recorded at 12 months post intervention, proportions of patients engaging in recommended activities.

Ethical Considerations

This is a new research trial of an existing social networking tool already used in long term diseases but not yet specifically in COPD. Prior to introducing this to the entire clinical service, clinical effectiveness recommends changes are trialled on a smaller proportion of the patient population in order to understand the benefits of time and cost prior to full scale implementation.

As this is an intervention within a clinical service and the evaluation is conducted with NHS participants, on NHS properties therefore University ERGO (Ethics) and HRA full NHS ethics application has been sort. The Ethical review number will be on all patient facing documentation. This ethical review has evaluated the social and scientific value of the study. Further to this it ensures adequacy of patient information, the informed consent process, recruitment arrangements and access to information.

The service implementation and evaluation will also be presented at the Solent Adult service line, clinical effectiveness and audit group for Solent NHS Trust approval.

References

Beecham, J. and Knapp, M. **Costing Psychiatric Interventions. Discussion paper.** Chapter for *Measuring Mental Health Needs*. 1999. Ed Thornicroft, G.

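### Uptake is to be compared between arms, but the plan's only uptake measure depends on what was recommended and the recording tool belongs to one arm

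*Combined protocol and SAP*

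**What the plan says.** Uptake appears in four places, which do not agree.

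- **Secondary objectives:** the aim is to observe and understand how patients take up and use the GENIE recommendations. No comparator is named.
- **Analysis of Outcomes:** "patient uptake of the social activities is to be recorded on paper using the Genie tool and compared between groups". This is the only explicit between-arm comparison of uptake, and it speaks of social activities in general.
- **Table of Events:** a row for an uptake discussion or online survey is marked at 12 weeks and at the potential 1-year phase. It has no entry before the intervention.
- **Analysis Plan, 12 month follow up survey, item b):** uptake at 12 months is given as "proportions of patients engaging in recommended activities". No arms, threshold or test are given.

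On what each arm is offered, Selection and patient information says that randomised participants receive "normal clinical care (discharge planning with suggested activities), and the GENIE tool intervention, in the GENIE group", and that "this is in addition to usual clinical care". Of the alternatives to the maintenance class now open to patients leaving pulmonary rehabilitation, Implementation Design says "these options are currently limited or difficult to access in one place". Under Intervention, GENIE Stages 3 and 4 link the patient to a database of local resources and show the options on a map. Stage 1 asks patients to name the important people and activities in their network. At follow-up, the network diagrams are reviewed in the intervention arm only.

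**The concern.** A between-arm outcome should have the same meaning in both arms. Here the set of activities that can count depends on allocation: the GENIE arm has the usual-care suggestions plus whatever the tool adds. A usual-care patient who joins a walking group that nobody suggested might not count, while a GENIE patient who joins the same group from the map would. The recording method differs too, because the named tool is used in one arm.

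The second difficulty is the starting point. One recruitment route is patients who have already attended maintenance exercise for a year or more, and the Introduction foresees community groups replacing clinic classes. Continuing and swapping activities are therefore to be expected. GENIE Stage 1 gives the GENIE arm a record of existing activities; nothing equivalent is described for usual care.

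What is at stake is one of the document's own claims: "This evaluation aims to demonstrate the effectiveness and increase social interactions and community networks in the COPD population". A count tied to recommendations partly reflects how many suggestions were made, and it cannot show on its own that social activity rose.

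**Working it through.** **No plan figure to reproduce.** The documents give no uptake rate, list length or threshold. The recruitment target of 30 to 60 per group has no derivation.

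**Is there an arm-neutral measure elsewhere?** None is described. The network-diagram review is for the intervention arm. The optional health behaviour questionnaire covers diet, appetite, alcohol and smoking. The healthcare usage questionnaire counts service contacts, work loss and costs; its last question asks for spending on items such as club or gym membership, which is not a record of activities.

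**Illustration with total activity held equal.** Assume every patient, in either arm, does *m* activities out of *L* available, chosen without regard to any list. GENIE then has no effect on activity. For a list of *k* items:

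P(at least one activity is on the list) = 1 − C(L−k, m) / C(L, m)

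*L*, *m* and *k* are all assumptions. The usual-care list is set at 3 and the GENIE list at 6 or 10.

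For L = 40, m = 2, C(40,2) = 780:
- k = 3: 1 − 666/780 = 14.6%
- k = 6: 1 − 561/780 = 28.1%, a gap of 13.5 points
- k = 10: 1 − 435/780 = 44.2%, a gap of 29.6 points

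All scenarios, at-least-one definition:

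| L | m | usual care (3) | GENIE (6) | gap, points | GENIE (10) | gap, points |
|---|---|---|---|---|---|---|
| 40 | 1 | 7.5% | 15.0% | 7.5 | 25.0% | 17.5 |
| 40 | 2 | 14.6% | 28.1% | 13.5 | 44.2% | 29.6 |
| 40 | 3 | 21.4% | 39.4% | 18.1 | 58.9% | 37.6 |
| 20 | 1 | 15.0% | 30.0% | 15.0 | 50.0% | 35.0 |
| 20 | 2 | 28.4% | 52.1% | 23.7 | 76.3% | 47.9 |
| 20 | 3 | 40.4% | 68.1% | 27.7 | 89.5% | 49.1 |

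Gaps are taken before rounding. They run from 7.5 to 49.1 points.

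**Chance of a false positive.** The calculation uses a normal-approximation test of two proportions at an assumed two-sided 5% level. For L = 40, m = 2, the chance of p < 0.05 in favour of GENIE is 24% with 30 per arm and 44% with 60 (lists 3 v 6), or 72% and 96% (lists 3 v 10). These use the full recruitment range; an optional 12-month sample would be smaller.

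**Other definitions of the same phrase.**
- Mean share of the list taken up: the expectation is m/L in both arms, for example 2/40 = 5.0% v 5.0%. The artefact is 0.
- All listed activities taken up, L = 20, m = 3: 1/C(20,3) = 1/1140 = 0.09% for a list of 3, and 0% for a list of 6. The artefact is nil or slightly reversed.
- Equal lists (3 v 3), at-least-one definition: the artefact is 0.

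**After the fix.** With any or total activity asked in the same way in both arms, the expected difference under this model is 0 in every row.

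**The case against.** The strongest reply is that the plan contains no complete scoring rule, so no bias is proven. Item b) may be an ordinary descriptive rate for the GENIE arm, as the secondary objective suggests. The sentence that does compare groups says social activities, and Future work uses similar wording for the 1-year survey. This stands: the artefact arises only if the item b) numerator is carried into the comparison and read as at least one. It does not remove the point. The comparison is planned, uptake is not otherwise defined for it, and the recording tool is used in one arm only.

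The second reply is that listing an activity is how GENIE is meant to work, so part of an observed gap could be real. That is also fair. A reader might give each listed activity the same chance of attendance and call the whole resulting gap spurious; with chances of 5% to 15% and lists of 3 v 8, that gap is 19 to 34 points. The calculation does not hold total activity equal: at 10%, the expected number of listed activities attended is 3 × 0.10 = 0.3 against 8 × 0.10 = 0.8. It is therefore not used here.

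Third, a reader might infer that neither arm has any record of earlier activity, since the Table of Events shows none. GENIE Stage 1 does record it in the GENIE arm, at least for the activities that patients name. The gap is in usual care.

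**Conclusion.** The point holds in conditional form. The plan compares uptake between arms without defining it, names a tool that one arm uses, and offers in its Analysis Plan only a measure whose countable activities depend on allocation. Under an at-least-one reading, the GENIE arm can score higher with no difference in total activity.

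The range of 7.5 to 49.1 points shows that the artefact need not be trivial; it is not an estimate for this trial. It rests on assumed lists of 3 v 6 to 10, 20 to 40 available activities, and 1 to 3 done per patient. That the GENIE list is longer is a reasonable inference from the description of both arms, not a documented figure.

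A reader might conclude that the GENIE arm must score higher, or that the trial's main results are affected. The documents support neither. Direction and size depend on a definition that is not given. Uptake lies outside the cost-utility, CAT and psychological analyses, and the 12-month phase is optional. The change should be made, but the trial's primary analyses do not depend on it.

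**What to change.** 1. For the between-arm comparison, define uptake as taking part in any social, community or exercise activity that the participant was not doing at baseline, whoever suggested it.
2. Ask one identical short item in both arms at baseline, at 12 weeks and, if that phase runs, at 1 year. Do not use the GENIE tool as the recording instrument for this comparison.
3. Compare the proportion with at least one new activity, and the number of current activities adjusted for the baseline number.
4. Report uptake of GENIE recommendations descriptively within the GENIE arm only, stating how many recommendations were made and what counts as engaging. This serves the secondary objective as written.
5. Align Secondary objectives, Analysis of Outcomes, the Table of Events with Future work, and the 12-month section of the Analysis Plan.

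The cost is about a minute of participant time at each assessment and a changed definition. The uptake figure may look less favourable. For anyone already enrolled, the baseline item cannot be collected prospectively, so the new-activity comparison should be limited to participants who have it.

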(English) EQ-5D-5L Pdf

Health care utilisation questionnaire

Healthcare Usage Questionnaire

We would like to know how much use you have made of the health and social services over the last 3 months. If you are not exactly sure, we would rather have your best guess than no information at all.

Please answer every question, even if the answer is 'No'.

1) Over the last 3 months, if, and how many times, have you used any of the following:

Type of Service	No	Yes	If yes: Number of visits
GP		At home	
		In the surgery	
		On the phone	
Practice nurse		At home	
		In the surgery	
		On the phone	
Social worker		At home	
		In the facility	
		On the phone	
Visit at home from a community nurse or Dr			
Specialist community clinic –with consultant			
NHS Smoking Cessation clinic			
Other (describe)			

2) Hospital outpatient visit for breathing related issues

Episode*	Name of the hospital	Reason for appointment	Specialty of Department	Number of appointment*
1 st				
2 nd				
3 rd				
4 th				

*Episode means a visit or group of visits related to a particular problem. Please write down how many appointments you have had for each episode

3) Accident and Emergency for COPD / breathing issues

Episode	Name of the hospital	Reason for visit	Referral from
1 st			GP
			Outpatient
			Self-referral
2 nd			GP
			Outpatient
			Self-referral
3 rd			GP
			Outpatient
			Self-referral
4 th			GP
			Outpatient
			Self-referral

4) Hospital Inpatient for COPD / breathing and chest issues

Episode	Name of hospital	Ward Speciality	Reason for admission	No of nights*
1 st				
2 nd				
3 rd				
4 th				

*If you were treated as a day patient (day case), then please write 0 under "number of night"

5) Are you currently in paid employment?

No (please go to question 5b) Yes (please go to question 5a)

5a If yes, how many days have you been absent from work because of COPD in the last 3 months?
Please state how many days 5b If you are not employed:,

In the last 3 months have you had to stop work completely due to your COPD disease

No

Yes

6) Over the last 3 months has a relative or friend taken time off work to look after you?

No

Yes, how many days

7) In the last 3 months, approximately how much additional money have you spent on travel (taxi car park fees and public transportation because of your COPD disease)

None

Yes, I spent £ _____

8) If you would like to tell us about any other costs incurred because of your COPD over the last 3 months (club/gym membership, employing extra help, buying extra equipment, food and meal delivery), please write them here.

No

Yes I spent £ _____ please give details _____

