Following the training, the participants will be given the tools required to roll out the intervention

- Paper and web-based concentric circles with typologies and support suggestions
- Guidebook on how to deliver GENIE
- Access to the database and website

Identification, enrolment and randomisation

[figure not shown]

Table of Events

	Consent and Randomisation	Pre – intervention data collection	12 weeks post intervention data collection (+/- 1 week)	Potential 1 year follow up phase
Consent form discussion and taking informed consent	x			
Randomisation (Block)	x			
EQ-5D		X	x	x
Health Care Utilisation Questionnaire		X	x	x
Socio-economic background / demographic data		X		
Gender		X		
Disease severity (FEV1)		X		
HEIQ (Self-management)		X	x	
Optional Health behaviour questionnaire		x	x	x
CAT		X	x	x
Gad-7 /		X	x	
PHQ-9		x	x	x
Uptake discussion / online survey			x	x

Quality Assurance

The delivery of the intervention will be taped in as many cases as consented to ensure that the intervention is delivered consistently by the research team to all patients. The tape recording is for quality assurance, and is not intended for research utilisation or publication.

Future work

The participants included in this initial 3 months of the study could be followed up again in 1 year (12 months) to ascertain longer term outcomes and longevity of connections made. This element could consist of a paper or online survey to understand the uptake rates of the social actives 1 year on, and further investigation into QOL, **healthcare use and the option of assessing health behaviours.** All participants would be given the option of continuing for a year, and therefore those who continue would be decided by participant preference to remain in the study.

Analysis Plan

Primary Outcomes

Descriptive statistics of the cohort,

Descriptive statistics of the cohort will be reported including but not limited to; age, gender, severity of disease then the analysis will be broken down into 5 distinct sections;

- a) Pre and post intervention cost utility analysis for the usual care group and the intervention group.
- b) Comparative group - pre and post cost utility analysis; calculated cost per QALY (quality adjusted life years) gained and cost of healthcare usage per patient– usual care group at 3 months after leaving the COPD service compared with the post intervention group 3 (+/- 1 week) months after leaving the COPD service, with significance.

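### The usage form's fixed three-month recall is about a week longer than the 12-week follow-up, so some pre-intervention contacts are counted as outcome; anchor the form to the dated study visit

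*Combined protocol and SAP*

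**What the plan says.** The primary objective (Objectives, Primary objectives) includes healthcare utilisation. Items (a) and (b) of the Analysis Plan turn it into cost-utility analyses and a cost of healthcare usage per patient at 3 months.

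The data come from the Healthcare Usage Questionnaire in the Appendices. Its heading reads "We would like to know how much use you have made of the health and social services over the last 3 months", and item 1 repeats the period: "Over the last 3 months, if, and how many times, have you used any of the following". Items 5a to 8 also refer to the last three months, apart from the opening question on current employment. Items 2 to 4 (outpatient, A&E, inpatient) state no period and rely on the heading. No version tied to a visit date is given.

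On timing, the Selection and patient information section says of the randomisation visit: "Baseline questionnaires will also be administered at this visit". For follow-up it says: "The follow up period will commence 3 months (12 weeks) (+/- 1 week) from the day the GENIE tool was initially delivered". The Table of Events also gives 12 weeks ±1 week. The Three monthly follow up section carries ±1 week in its title, but its text says "these will be repeated at 3 months post intervention (+/- 2 week").

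The row "Health Care Utilisation Questionnaire" in the Table of Events is marked before the intervention, at 12 weeks and at a potential 1-year phase. Under Future work, participants "could be followed up again in 1 year (12 months) to ascertain longer term outcomes".

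**The concern.** A follow-up measure of use should cover the time from the intervention to the visit. Here the recall length is fixed and the time since intervention is not: it is nominally shorter than the recall and varies within the visit window. Contacts from before GENIE delivery, which GENIE cannot have influenced, are therefore recorded as post-intervention use, and the same contacts have already been reported at baseline. If a visit takes place later than the recall length, the first days after the intervention are missed instead.

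At stake are the precision of the healthcare-use comparison in a trial of 30 to 60 participants per group, the meaning of the reported cost per patient after leaving the service, and any result expressed as a percentage change or ratio.

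**Working it through.** The plan gives no figure of its own to reproduce; the check is date arithmetic.

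**Inputs**
- Recall R: 3 months, about 91 days (89 to 92 by calendar). Source: questionnaire heading.
- Visit day V: 84 nominal, 77 to 91 with ±1 week. Source: Selection and patient information; Table of Events.
- Wider window: 70 to 98 days if ±2 weeks is applied to 12 weeks. Source: Three monthly follow up.
- Day 0: GENIE delivery, taken as the same visit as randomisation and baseline. Source: Selection and patient information.

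**Overlap = R − V**

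| Visit | V (days) | R − V (days) | Share of recall |
|---|---|---|---|
| 11 weeks | 77 | 14 | 14/91 = 15.4% |
| 12 weeks | 84 | 7 | 7/91 = 7.7% |
| 13 weeks | 91 | 0 | 0% |

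The calendar range puts the 12-week overlap at 89 − 84 = 5 to 92 − 84 = 8 days. Under ±2 weeks counted from 12 weeks, the extremes would be 91 − 70 = 21 days of overlap and 98 − 91 = 7 post-intervention days missed. If that window is counted from 91 days instead, the earliest visit is day 77, with 14 days of overlap.

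**Difference in means at day 84.** Let both arms have daily rate λ before day 0, and rates λ₁ (GENIE) and λ₀ (usual care) afterwards. Expected counts are 7λ + 84λ₁ and 7λ + 84λ₀. The difference is 84(λ₁ − λ₀): the overlap cancels, and all 84 post-intervention days are captured.

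**Ratio or percentage effect.** If λ = λ₀ and the true relative reduction is d, the observed reduction is 84d/91 = 0.923d, a shrinkage of 7.7%.

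**Noise.** For the same absolute difference, the recall is 91 days instead of 84.
- Poisson counts: SD grows as the square root of the window, √(91/84) = 1.041, about 4% higher.
- Stable between-person differences dominating: SD grows in proportion to the window, 91/84 = 1.083, about 8% higher.

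**Pre/post change.** Baseline covers days −91 to 0 and follow-up covers days −7 to 84. The shared week cancels in the subtraction, leaving days 0 to 84 compared with days −91 to −7. The result is blurring, with the last pre-intervention week dropping out of the change; the change itself is not inflated.

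**One-year phase (secondary).** With forms at day 84 and month 12, the uncovered time is 365 − 84 − 91 = 190 days, or 52% of the year, roughly months 3 to 9.

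**The case against.** The strongest reply is that randomisation already protects the main comparison. The extra days add the same expected amount to each arm and drop out of the difference in mean cost that feeds the cost per QALY. A reader might infer that the arm difference itself shrinks by 8% or more; the algebra above does not support that for a difference in means. The shortfall against a full 91-day effect comes from visiting at day 84, and a form anchored to the visit would show the same expected difference. This part of the reply stands.

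It also stands that the mismatch is about one week in thirteen and near zero at 13 weeks, that the data are self-reported and the form accepts approximate answers, and that rehabilitation sessions are not a listed service and could enter only under the free-text category. Nor does any planned analysis add the baseline and follow-up totals, so reporting the overlap on both forms does not inflate a sum. A fixed recall has the merit of the same nominal window on every form.

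The noise, the diluted ratios and the mislabelled cost per patient remain. Cancellation also needs similar visit timing in the two arms, which the text leaves loose. Follow-up is counted from GENIE delivery, a date usual-care participants do not have, and Analysis Plan item (b) attaches ±1 week only to the intervention group.

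A reader might further infer that a 12-month cost estimate is undermined. The documents plan none. The phase is optional future work, and the section headed 12 month follow up survey lists only CAT and activity uptake. Analysis of Outcomes does say "Medication, health service use will be measured at baseline, 3 months post implementation and follow up", but no 12-month total or cost per QALY is specified.

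**Conclusion.** The mismatch is real and modest. At the nominal visit about 7 of 91 recalled days precede the intervention; within ±1 week this runs from about 14 days to about 0. It does not bias the expected difference in mean use or cost between arms if visit timing is alike. Its costs at day 84 are an SD about 4 to 8% higher for an unchanged absolute difference, about 8% shrinkage of ratio or percentage effects, contacts from before discharge in the cost per patient, and an overlap week reported on both forms.

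This rests on participants taking three months literally, on equal pre-intervention rates in the arms, and on randomisation, baseline and GENIE delivery sharing one visit. The Table of Events lists consent and randomisation in a separate column from pre-intervention data collection, so strictly the overlap is with time before delivery. The documents give no contact rates, so the effect on cost in pounds cannot be stated.

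The point justifies a change to the form; it does not invalidate the 3-month comparison. If the optional 12-month survey uses the same form, it supports only a comparison of use in about months 9 to 12.

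**What to change.** - On the 3-month form, replace the fixed period in the heading and in every item that states it with *since your study visit on [date of baseline/randomisation visit]*. Add the same words to items 2 to 4. Use this anchor in both arms.
- Record the baseline and follow-up dates. In the Analysis Plan, state that 3-month use and cost are multiplied by 84 / (days between the two visits). Scale the baseline form, which keeps its three-month recall, by 84/91, so that pre/post comparisons use equal periods.
- Reconcile ±1 week with ±2 weeks, and state that the window runs from the same visit in both arms.
- If the form is used at 12 months, label the result as use in the last three months and derive no annual total from it.

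The cost is one date field, a reworded form and a few lines in the plan, with no added visits. The small downside is that recall length varies between participants and sparse counts have to be scaled. In return, the overlap is zero at any visit within the window, and no early post-intervention days are lost at a late one.
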